19.7.1.1. Derivations Related to Grading of Ocular AEs

The grading of Ocular AEs is based on changes in visual acuity (VA delta). In this study, the VA may be measured with or without correction, and it should always be non-missing. The same method which is used to measure VA at baseline (uncorrected or corrected) should be used throughout the study on all eye exams for an individual subject.

The 2 measurement methods (corrected, uncorrected) must not be mixed in making the determination of the VA delta. In cases where multiple methods are used within a subject in the study, the baseline measurement method will determine which of the post-baseline assessments can be used to assign a VA delta, and which should result in a VA delta of “cannot assess”. If no VA delta can be assigned, then the VA Grade will be missing. For example, if a subject’s data includes a baseline exam VA (uncorrected), a post-baseline exam 1 VA (uncorrected), and post-baseline exam 2 VA (corrected), then a VA delta and VA Grade can be assigned to only the post-baseline exam 1 result. The post-baseline exam 2 result can not be assessed for VA delta, and the associated VA Grade would be missing.

In cases where VA was not done or measured consistently for a subject but BCVA was done consistently throughout, the BCVA data may be used for VA grading. For example, if VA is missing at baseline, the baseline BCVA and post-baseline BCVA measurements may be used to assess changes in visual acuity. However, this is a compromise to the original study plan, as BCVA is a more lenient measure of change. The methods of assigning the VA delta and VA Grade are otherwise the same as when VA is used (as described above).

Non-standard visual acuity data should be converted to standard values prior to analysis. Visual acuity measurements which include special characters such as ‘+’ or ‘-’, with or without an associated number, should be stripped of the special characters and the numeric part of the value should be used as is. In addition, the numeric part of the value should be converted to a standard value, if necessary, by rounding down. Table M provides some examples.

Details of the grading process follow.

Table M. Conversion of Visual Acuity Data from Non-Standard to Standard Values

Source data	Derived Value for Analyses
20/32	20/30
20/30 +	20/30
20/30 +2	20/30
20/30 -	20/30
20/30 -2	20/30
20/30 -2 +2	20/30

Protocol Table 12 describes the grading of ocular AEs based on changes from baseline in visual acuity (VA) or best corrected visual acuity (BCVA). It is reproduced for convenience in Table N. Cases in which a subject’s baseline vision was recorded as better than 20/20 will be grouped with the 20/20 line of Table N for the purpose of assessing post-baseline changes.

Table N. Visual Acuity Grading Chart

Baseline vision [1]	Grade 1 [2]	Grade 2 [3]	Grade 3 [3]	Grade 4
20/20	20/20	20/25 (1) 20/30 (2) 20/40 (3)	20/50 (4) 20/60 (5) 20/70 (6) 20/80 (7) 20/100 (8) 20/125 (9)	20/200 or worse
20/25	20/25	20/30 (1) 20/40 (2) 20/50 (3)	20/60 (4) 20/70 (5) 20/80 (6) 20/100 (7) 20/125 (8)	20/200 or worse
20/30	20/30	20/40 (1) 20/50 (2) 20/60 (3)	20/70 (4) 20/80 (5) 20/100 (6) 20/125 (7)	20/200 or worse
20/40	20/40	20/50 (1) 20/60 (2) 20/70 (3)	20/80 (4) 20/100 (5) 20/125 (6)	20/200 or worse
20/50	20/50	20/60 (1) 20/70 (2) 20/80 (3)	20/100 (4) 20/125 (5)	20/200 or worse
20/60	20/60	20/70 (1) 20/80 (2) 20/100 (3)	20/125 (4)	20/200 or worse
20/70	20/70	20/80 (1) 20/100 (2) 20/125 (3)	N/A	20/200 or worse
20/80	20/80	20/100 (1) 20/125 (2)	N/A	20/200 or worse
20/100	20/100	20/125 (1)	N/A	20/200 or worse
20/125	20/125	N/A	N/A	20/200 or worse
20/200	20/200	N/A	N/A	Worse than 20/200

[1] With or without correction, based on patient's daily functional distance vision

[2] No change in vision from baseline. Grade 1 is the same as screening (baseline) from a VA perspective. The Grade 1 Clinical Ocular AE will be an event when the AE is present (e.g., keratopathy) but there is no change in VA from baseline and the subject has little to no symptoms. If the AE is not treated aside from using artificial tears, then it would be considered Grade 1.

[3] Visual acuity measurement and delta, where delta = number of line changes from baseline.

Clinical Ocular AE grading will be determined based on visual acuity (VA) change from screening (baseline). This will be done as follows:

- Determine baseline VA for each eye. Subject should have the VA measured with or without glasses depending on the subject’s requirement for daily use for distance vision. Use Table L and identify the row of the baseline vision for each eye.
- Subsequent eye exam VA (obtained under same conditions as screening (baseline)), determine if a change in vision is present. If so, use the row in Table L identified in Step 1, to locate the current VA and determine the number of line-of-vision-change from baseline for each eye; this is expressed as the number in parenthesis. Also note the grade of the VA for each eye.
- Between the two eyes, determine the eye with greater line-of-vision-change from baseline (delta). The Clinical Ocular AE grade for the subject is the grade of the worse (delta) eye. See Examples 1 and 2 in Table M.
- In the event both eyes have the same delta, then the Clinical Ocular AE grade comes from the eye with the worse new vision. See Example 3 in Table O.

Table O. Examples of Clinical Ocular AE: Keratopathy

	Baseline (CC)	New VA (CC)	Lines VA Change	VA Grade	Clinical Ocular AE Grade
Example 1					
OD	20/20	20/50	(4)	3	Grade 3
OS	20/40	20/70	(3)	2	
Example 2					
OD	20/60	20/125	(4)	3	Grade 3
OS	20/100	20/200	(2)	4	
Example 3					
OD	20/30	20/100	(5)	3	Grade 4
OS	20/60	20/200	(5)	4	

19.7.2. EYE SYMPTOM QUESTIONNAIRE

The Eye Symptom Questionnaire (ESQ) will be completed at screening and on other occasions when the full ophthalmologic exam is performed. The ESQ collects information related to the following items:

- Dry Eyes (none, mild, moderate, severe)
- Eye Pain (none, mild, moderate, severe)

- Blurred Vision (none, mild, moderate, severe)
- Photophobia (none, mild, moderate, severe)
- Other, specify (none, mild, moderate, severe)
- Steroid Use (Taken as directed, used most of the time, did not use most of the time, used every day continuously, did not use at all, other)

A summary table by treatment arm will present the number and percentage of subjects who reported each eye symptom, overall and by severity, during each cycle and at the Safety Follow-up visit. Each unique symptom report will be counted only in the cycle in which it began. The severity of the worst post-baseline assessment and the final assessment will also be tabulated. A data listing will be provided.

A separate table will display the number and percentage of subjects who had >25%, >50%, >75%, or 100% of ocular symptom-free days during treatment. The calculated number and percentage of symptom-free days by subject will be provided in a listing.

Also, a swimmer lane plot which shows the duration of any post-baseline ocular symptom during the period from Day 1 through the end of the Safety Follow-up period will be produced. The plot will display a bar connecting any consecutive visits at which a symptom was reported, or a simple bracket or narrow line around individual visits at which a symptom was reported. Important treatment events (e.g., day of first dose, day of last dose or decision to end treatment, day of Safety Follow-up visit, day of each study drug infusion for AGS-16C3F subjects) will be marked on the subject's timeline.

A summary of ocular steroid use by cycle and at the final assessment will be produced.

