#### **5.6.5.1 Symptom Based Ocular AEs**

Ocular symptoms reported by the subject during clinic visits will be graded per CTCAE v4.03 (i.e., symptom based assessment) and this will guide the treatment decision for that visit and the necessity for a follow up ophthalmology consult.

An Eye Symptom Questionnaire (ESQ) will be administered at every visit in the oncology clinic. Please see the Study Guide for the form and for complete instructions. During screening, the ESQ will be completed for both Cancer Treatment History and Screening sections.

The ocular symptom AEs must be collected in the eDC system.

If a subject reports ocular symptoms, the following guidelines may be used:

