Sponsor will be followed until resolved or considered stable. If a treatment-related adverse event is not resolved but is considered stable at the safety follow-up visit, this must be documented in the source documents.

The following attributes must be assigned by the investigator: description; dates of onset and resolution; severity; assessment of relatedness to investigational product, action taken, serious status and criteria.

It will be left to the investigator's clinical judgment whether or not an AE is of sufficient severity to require the subject's removal from treatment. However, the Medical Monitor will be consulted prior to the subject being discontinued from study for safety reasons.

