19.1.1. ALL TEAEs

Incidence of TEAEs will be presented by treatment group, System Organ Class (SOC), and Preferred Term (PT), and will also be broken down further by maximum severity and relationship to study drug. In these tables, SOCs will be presented alphabetically, and PTs will be presented by decreasing frequency of all events in a PT in the AGS-16C3F arm within SOC.

The number and percentage of subjects who reported TEAEs, possibly treatment-related TEAEs, and TEAEs of CTCAE Grade ≥ 3 will also be summarized by treatment group and presented by PT in the order of descending incidence in the AGS-16C3F group.

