19.1.6. ADVERSE EVENTS OF SPECIAL INTEREST

Ocular adverse events and diagnoses which are entered as AEs will be reported on the general tables of AEs. A listing of eye-related TEAEs will be provided.

Ocular toxicities based on ophthalmology exams will be reported on the Eye Exam eCRFs and will be graded using the study specific ocular criteria. These will be tabulated separately from the general AE tables. See Section 19.7.1 and Section 19.7.2 for planned analysis and reporting.

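### On its most natural reading, the by-cycle Eye Symptom Questionnaire table counts onsets only, and no output in the SAP text gives the prevalence of each symptom by severity and cycle (minor)

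*SAP*

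**What the plan says.** SAP 19.7.2 describes a summary by treatment arm of the number and percentage of subjects with each ESQ symptom, overall and by severity, "during each cycle and at the Safety Follow-up visit". The next sentence sets the counting rule: "Each unique symptom report will be counted only in the cycle in which it began". The SAP does not define a unique symptom report, and the ESQ items it lists carry no start date.

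The same section also plans a tabulation of worst and final severity, a table of symptom-free days, a listing and a swimmer plot. Of the plot it says: "The plot will display a bar connecting any consecutive visits at which a symptom was reported".

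Ocular symptoms are recorded as adverse events too. Protocol 5.6.5.1 states: "The ocular symptom AEs must be collected in the eDC system". The attributes the investigator assigns to each adverse event (Protocol 5.7.1) include "description; dates of onset and resolution; severity". In the SAP these events enter the general TEAE tables, which "will also be broken down further by maximum severity and relationship to study drug" (19.1.1), and 19.1.6 adds: "A listing of eye-related TEAEs will be provided".

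**The concern.** The table's layout promises a picture of symptoms over time, whereas the counting rule delivers new symptoms over time. The two differ whenever symptoms last longer than a cycle. Under an onset rule the by-cycle figures can fall although no symptom has resolved, and a reader of the table could take fewer onsets for recovery. The Safety Follow-up column, which bears most directly on reversibility, would leave out symptoms carried over from treatment.

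This matters because Protocol 1.4 names ocular toxicity as the compound's distinctive toxicity, reported in 12 of 13 Phase 1 subjects at 1.8 mg/kg. Protocol 5.6.5.1 uses symptoms reported at a visit to guide treatment at that visit. How many subjects are symptomatic in a cycle, and how severely, is therefore a question the safety summary should answer.

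**Working it through.** The plan gives no figure to reproduce. The check has three parts.

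**1. Which reading fits.** A questionnaire entry does not begin in a cycle; an episode does. The swimmer plot in the same section also treats a symptom as running across visits. Both favour the episode reading, and so an onset count. The SAP does not say whether a worsening in severity starts a new report.

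**2. Does another output fill the gap?** Each ocular output in the SAP text was compared with four features.

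| Output | Each symptom | Severity | Per cycle | Present, not only new |
|---|---|---|---|---|
| ESQ by-cycle table, onset reading (19.7.2) | yes | yes | yes | no |
| ESQ worst and final severity (19.7.2) | implied | yes | no | at two derived timepoints |
| Symptom-free days (19.7.2) | no | no | no | yes, over the whole treatment period |
| Swimmer plot (19.7.2) | any symptom | no | timelines with infusions marked, no counts | yes |
| Eye-exam symptom table (19.7.1) | yes | no | multi-cycle intervals | no: first occurrence, plus a count of reports |
| Acuity grade; slit-lamp, IOP and fundus abnormalities (19.7.1) | signs, not symptoms | acuity graded | planned timepoints | yes |
| TEAE tables (19.1.1) | by preferred term | maximum | no | no |

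The ESQ and eye-related TEAE listings hold subject-level data but are not summaries. No row has all four features.

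**3. Size.** Under the onset reading, a symptom unchanged over L consecutive cycles is shown in 1/L of them: 100% at L = 1, 50% at L = 2, 25% at L = 4. For example, onset in Cycle 2 persisting through Cycle 6 gives L = 5 and a share of 1/5 = 20%.

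Anything further needs assumptions, because the documents give no durations. As an illustration, take dry eye in Cycle 6. The input from Protocol 1.3.1.2 is F = 7/13 (54% at 1.8 mg/kg). Assumed: F is a Phase 1 TEAE rate standing in for an ESQ rate, it is reached by Cycle K = 6, the onset hazard is constant, each subject has one onset, the mean duration is D cycles, nobody drops out, and severity is not modelled.

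- Hazard per cycle: h = 1 − (1 − F)^(1/K) = 1 − (6/13)^(1/6) = 0.121
- Shown in Cycle 6: h(1 − h)^5 = 6.3%
- Prevalence in Cycle 6: sum over j = 1 to 6 of h(1 − h)^(j−1) × (1 − 1/D)^(6−j)

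| D (cycles) | Shown | Prevalence | Ratio | Ratio range over variants |
|---|---|---|---|---|
| 1 | 6.3% | 6.3% | 1.00 | 1.00 |
| 1.5 | 6.3% | 10.2% | 1.61 | 1.50 to 1.67 |
| 2 | 6.3% | 14.2% | 2.24 | 1.98 to 2.42 |
| 3 | 6.3% | 21.3% | 3.35 | 2.82 to 3.77 |
| 4 | 6.3% | 26.6% | 4.18 | 3.47 to 4.80 |

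The variants are dry eye (7/13) or blurred vision (6/13), K = 4, 6 or 8, and single or recurrent onset. For recurrent onset, shown_c = (1 − prev_(c−1))h and prev_c = prev_(c−1)(1 − 1/D) + shown_c, with prev_0 = 0.

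**The case against.** The strongest objection concerns the reading. Safety Follow-up is not a cycle, so a rule tied to the onset cycle fits that column poorly. SAP 19.7.1 counts multiple reports per subject, which suggests that a report is an entry rather than an episode. With no start date on the listed items, the sentence may only mean that one report is not counted twice. The templates, which SAP 8 says set format and content, would settle this and are not available. This leaves real doubt, but the word for beginning still points to an episode, and under either reading the sentence needs a definition.

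A reader might infer that the SAP ignores persistent ocular toxicity. The documents do not support that. Acuity grade is tabulated at each planned timepoint, slit-lamp, IOP and fundus abnormalities at each planned visit, and the swimmer plot shows who has any symptom around each infusion. These are signs or uncounted timelines, so they narrow the gap without closing it.

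A reader might also take the ratios above as an estimate of understatement. They are not one: durations and onset timing are assumed, and a ratio of 1.00 is in the range. The no-dropout assumption is unrealistic. Phase 1 median treatment at this dose was 17.7 weeks, and 17.7/3 = 5.9 cycles, so about half the subjects would be off treatment near Cycle 6. Only the 1/L result is exact, and it is conditional on the onset reading.

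Finally, the SAP ties ESQ completion to screening and "on other occasions when the full ophthalmologic exam is performed", while current Protocol 5.6.5.1 has it at every oncology clinic visit. That looks like a contradiction, but the SAP was written on protocol version 4.0, whose wording is not visible, so it is not counted as an error here.

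**Conclusion.** The point holds in limited form. On its most natural reading the counting rule makes the only ESQ table laid out by cycle and severity a table of onsets, and nothing else described in the SAP text gives prevalence by symptom, severity and cycle. A symptom lasting L cycles is shown in 1 of L; the actual gap is unknown and could be nil if symptoms resolve within a cycle.

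The conclusion rests on the episode reading and on the SAP text without its templates. Severity is minor: this is descriptive safety reporting, SAP 19 plans no between-arm safety tests unless a section specifies one, the data remain in the listings, and PFS is unaffected.

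**What to change.** In SAP 19.7.2, replace the counting sentence with:

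> A subject is counted in every cycle, and at Safety Follow-up, in which the ESQ reports the symptom, at the worst severity reported in that period; the denominator is subjects with at least one ESQ in that period. New-onset counts are shown as separately labelled rows. An ESQ completed before dosing at a Day 1 visit belongs to the cycle just ended.

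The pre-dose ESQ at Cycle 1 Day 1 stays baseline under SAP 6.3. Map axitinib planned-day visits to the matching cycle, since SAP 6.4 identifies those visits by study day.

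Keep all scheduled and unscheduled ESQs in the main table. Protocol 5.2.6.1 and 5.2.6.2 require both, SAP 19.7.1 includes planned and as-needed assessments in eye summaries, and unscheduled visits may be where symptomatic subjects appear. Footnote that AGS-16C3F subjects have extra PK-day ESQs in Cycle 1 (Days 2, 4, 15) and Cycle 4 (Days 65, 67, 78), which gives that arm more opportunities to report. A supportive display restricted to visits common to both arms is optional.

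The cost is SAP wording and one longer, reprogrammed descriptive table with the cycle mapping for axitinib. Under the current protocol's visit schedule, no new data are needed.

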20. PHARMACOKINETIC ANALYSIS

The Sponsor pharmacokineticist will perform the analyses described in Protocol Section 7.6 and will provide the plasma concentration data and PK parameter estimates to QuintilesIMS.

Descriptive statistics for plasma concentration data will be provided by visit and planned timepoint. Descriptive statistics for the PK parameter estimates will be provided by visit.

Plasma concentration data and PK parameter estimates will be listed.

21. ANTI-DRUG ANTIBODY

Blood samples for testing anti-AGS-16C3F antibody level will be collected from subjects who receive AGS-16C3F on C1D1, C4D1, C6D1, and every 12 weeks thereafter until treatment is discontinued.

The number and percent of subjects (incidence) of anti-drug antibody formation to human native antibody (AGS-16C3) and to antibody drug conjugate (AGS-16C3F) will be tabulated at each timepoint and at each subject's final assessment.

22. DATA NOT SUMMARIZED OR PRESENTED

These domains and/or variables will not be summarized or presented on listings, but will be available in the clinical study database, SDTM and/or ADaM datasets, or in the non-computerized study report appendices.

Subject data

-
- Comments
 - Demographics: If female, is the subject a woman of childbearing potential? (Y/N)
 - AGS-16C3F drug administration: Infusion start time, infusion stop time, infusion rate, infusion unit
 - Axitinib drug administration data: Dispensing and return information, miscellaneous other.
 - Survival status: If alive or unknown, will this subject's survival follow-up continue? (Y/N). If no, please indicate reason (Lost to follow-up/ Withdrew consent). Date lost to follow-up or date consent withdrawn
 - SAEs: Date of death, cause of death, date of hospital admission/discharge, study drug administration lot number, start/stop/ongoing, dose, unit, frequency (as collected on the SAE eCRF).
 - Details of specialized informed consent, including:
 - Pre-Screen Informed Consent
 - Subject consent to optional tumor sample collection as part of SOC while on study
 - Subject consent to bank leftover tumor tissue samples for future research testing to learn more about the study drug
 - Subject consent to bank leftover tumor tissue samples for future research testing to explore how to treat cancer
 - Randomization number

CRF fields designed primarily for data management purposes or as CRF completion instructions

- CRF fields designed to track what procedures were performed or what CRFs should have been completed.
 - Indicate what unscheduled CRFs were completed
 - Indicate if chemistry tests were performed? (Y/N)
 - Indicate if hematology tests were performed? (Y/N)
 - Indicate if coagulation tests were performed? (Y/N)
 - Indicate if urine tests were performed? (Y/N)
 - Was a serum pregnancy test done? (Y/N)
 - Indicate if PK blood draw was performed? (Y/N)
 - Indicate if ADA blood draw was performed? (Y/N)
 - Was bone imaging performed? (Y/N)
 - Was a brain scan performed? (Y/N)
- CRF fields designed to account for the presence/absence of other recorded data on a CRF.
 - Did subject meet all protocol eligibility criteria? (Y/N)
 - Was any surgery performed for malignancy prior to enrollment? (Y/N)
 - Was any radiotherapy given for malignancy prior to enrollment? (Y/N)
 - Physical examination (normal/abnormal) and related instructions for recording further data on other CRFs
 - Ocular diagnoses at this visit? (Y/N)

-
- Events CRF
 - CRF fields designed to facilitate the tracking of collected samples or follow-up activities.
 - PK Requisition number
 - ADA requisition number
 - SAE: Date Agensys notified of report
 - SAE: Site awareness date
 - SAE: Is a hospital discharge summary available? (Y/N)
 - SAE: Was an autopsy performed? (Y/N)
 - CRF fields designed to help track subject participation.
 - Will the subject continue another dosing cycle? (Y/N)

APPENDIX 1. QUINTILES GLOBAL BIostatISTICS STANDARD OUTPUT CONVENTIONS

ABBREVIATIONS

ASCII	American standard code for information interchange file format
CGM	Computer graphics metafile
ODS	Output Delivery System
RTF	Rich text file format

INTRODUCTION

This Appendix applies to standards used for outputting tables, listings and figures. It is intended to provide specifications to guide the statistician or statistical programmer in setting up specifications for programming tables, listings and figures. These standards should be used in the absence of customer specific standards.

If the mock shells for this study appear to depart significantly and consistently from these standards in any way, please check with the project statistician for a resolution prior to programming.

OUTPUT FILE NAMING CONVENTIONS

- File names should only consist of uppercase letters, lowercase letters, digits (0 to 9) and underscores. A period should only be used to indicate a separator between the file name and the extension. No spaces, other special characters or punctuation marks are permitted.
- As far as possible, output files should be in RTF format, although .DOC files are also permitted. The program, program log and output file name should reflect the type and number of the statistical output. If this is not possible, then the output name should be at least as descriptive as possible.
- A prefix can be used to distinguish between a Table, Listing and Figure document ('T' for table, 'L' for listing and 'F' for figure). If there is only 1 digit in the number of the table, listing or figure in the place where 2 digits are possible, a leading zero should be added in the file name to make sorting consistent with the sequence (e.g., T14_3_01_1.RTF).

PAPER SIZE, ORIENTATION AND MARGINS

- The size of paper will be Letter for the United States, otherwise A4.
- The page orientation should preferably be landscape, but portrait is also permitted.
- Margins should provide at least 1 inch (2.54 centimeters) of white space all around the page, regardless of the paper size.
- The number of columns per page (linesize) should be 145 for A4 and 134 for Letter.
- The number of rows per page (pagesize) should be 49 for A4 and 51 for Letter.

FONTS

- The font type 'Courier New' should be used as a default for tables and listings, with a font size of 8. The font color should be black. No bolding, underlining italics or subscripting should be permitted. Try to avoid using super-scripts, unless absolutely necessary. Single spacing should be used for all text.
- Figures should have a default font of "Times Roman", "Helvetica", or "Courier New".
- This can be achieved by using the following options in SAS.
 - o goptions
 - o gunit = pct
 - o cback = white
 - o colors = (black)
 - o hby = 2.4
 - o ftext = "TimesRoman"
 - o htext = 2.5
 - o device = cgmof97l
 - o gaccess = gsasfile;
 - o filename gsasfile "....cgm";

HEADER INFORMATION

Headers should be defined as follows:

- The header should be placed at the top of the page (same place on each page) regardless of the size or orientation of the table or listing.
- The customer name should appear in row 1, left-aligned.
- The output page number (page x of y) should appear in Row 1, right-aligned.
- The protocol number should appear in Row 2, left-aligned
- The output identification number should appear in row 3, centered.
- The output title should start in row 4, centered.
- The output population should appear in row 5, centered. The population should be spelled out in full, e.g., Intention-to-Treat in preference to ITT and should be placed in parentheses.
- Row 6 should be a blank line.
- Mixed case should be used for titles.
- The output titles should be designed so that they are arranged consistently through all outputs. For example, content (e.g., Vital Signs) followed by metric (e.g., Vital Signs Change from Baseline).
- Titles should not contain quotation marks or footnote references.
- The column headings should be underlined with a row of underscores ('_').
- Column headings spanning more than one column should be underlined and have underscores on either side of the title and should be centered.
- Column headings containing numbers should be centered.
- Column headings should be in sentence case.

-
- In general, the population count should appear in the column header in the form “(N=XXX)”.
 - “Statistic” should be the column header over n, Mean, SE, n (%) etc.
 - As a rule, all columns should have column headings.

TABLE AND LISTING OUTPUT CONVENTIONS

General

- The first row in the body of the table or listing should be blank.
- The left hand column should start in column 1. No indenting or centering of the output should occur.
- Rounding should be done for display purposes, after all calculations have been completed, using the SAS function ROUND.
- Numbers in tables should be rounded, not truncated.
- Alphanumeric output should be left aligned.
- Numbers should be decimal point aligned.
- Whole numbers should be right aligned.
- Text values should be left aligned.
- The first letter of a text entry should be capitalized.
- Listings of adverse events, concomitant medications, medical histories etc. should be sorted in chronological order, with earliest adverse event, medication or history coming first.
- The study drug should appear first in tables with treatments as columns.
- In general, only present totals (across treatment groups) at baseline/randomization, and do not present them post randomization, unless the customer specifically requests it.
- If possible, include 100% frequencies in the table shell, so that it is clear what the denominator is for percentage calculations.
- All listing outputs should be sorted (preferably by Treatment, Site Number and Subject Number).
- Do not use superscripts and subscripts.
- Exponentiation will be expressed using a double asterisk, i.e., mm³ will be written as mm**3.
- All variables that are output in the CRF (which have data present) should appear in the listings, along with all derived data appearing in the corresponding tables.
- The width of the entire output should match the line size.

Univariate Statistics

- Statistics should be presented in the same order across tables (i.e., n, Mean, SD, Median, Minimum, Maximum).
- Table statistics should line up under the N part of the (N=XXX) in the table header. All decimal points should line up. If the minimum and maximum are output on one line as Minimum, Maximum then the comma should line up with the decimal point.

- If the original data has N decimal places, then the summary statistics should have the following decimal places.
 - o Minimum and maximum: N
 - o Mean, median and CV%: N + 1
 - o SD: N + 2

Frequencies and percentages (n and %)

- Percent values should be reported inside parentheses, with one space between the count and the left parenthesis of the percentage. Parentheses should be justified to accept a maximum of 100.0 as a value and padded with blank space if the percent is less than 100.0. An example is given below.
 - o 77 (100.0%)
 - o 50 (64.9%)
 - o 0 (0.0%)
- Percentages will be reported to one decimal place. Percentages that are <100.0% but >99.9% will be presented as '>99.9%' (e.g., 99.99% is presented as >99.9%). Percentages that are <0.1% will be presented as '<0.1%' (e.g., 0.08% is presented as <0.1%). Rounding will be applied after the <0.1% and >99.9% rule.
- Percentages may be reported to 0 decimal places as appropriate (for example, where the denominator is relatively small).
- Where counts are zero, percentages of 0.0% should appear in the output.

Confidence Intervals

- As a rule confidence intervals are output to one place more than the raw data, and standard deviations and standard errors to two places more than the raw data.
- Confidence intervals should be justified so that parentheses displayed on consecutive lines of a table "line up".
- Boundary values of confidence intervals should be separated by a comma.
- Boundary values should be padded as necessary to accept negative values and to allow alignment of the decimal place.
- An example is given below:
 - o (-0.12, -0.10)
 - o (9.54, 12.91)

P-values

P-values should be reported to three decimal places, except values <1.000 but >0.999 will be presented as '>0.999' (e.g., 0.9998 is presented as >0.999); and values <0.001 will be presented as '<0.001' (e.g., 0.0009 is presented as <0.001). Rounding will be applied after the <0.001 and >0.999 rule.

Ratios

- Ratios should be reported to one more decimal place than the original data.

Spacing

- There must be a minimum of 1 blank space between columns (preferably 2).

Denominators

- If a different count other than the population count is used for a denominator (within the table) to calculate percentages, there should be a row in the table that identifies that number "n".

-
- Alternatively, a footnote should be included in each table with percentages to indicate the denominator for percentages.

Missing values

- A “0” should be used to indicate a zero frequency.
- A blank will be used to indicate missing data in an end-of-text table or subject listing.

FIGURE OUTPUT CONVENTIONS

- Figures should be provided in RTF files using the SAS Output Delivery System (ODS), as Computer Graphics Metafile (CGM) formatted graphical output generated by SAS.
- The CGM file itself should contain the title or footer.
- The image should be clear and of high quality when viewed in the Word document, and when printed.
- In general, boxes around the figures should be used.

FOOTNOTE INFORMATION

Footers should be defined as follows:

- A continuous line of underscores (‘_’) will follow the body of the table or listing prior to any footnotes at the bottom of the page.
- Table footnotes should be defined using compute statements in the proc report, and should appear directly after the body of the table.
- The program path and name and version number (if applicable) should appear as footnote 1 at the bottom of the page.
- The date/time stamp should appear as footnote 2 at the bottom of the page.
- Footnotes should be left-aligned.
- Footnotes should be in sentence case.
- Only “typewriter” symbols are permitted – e.g., “*”, “\$”, “#”, “@”, “&” and “+”.
- The choice of footnote symbols should be consistent. E.g. if you have the footnote “# indicates last observation carried forward” for one table, the same symbol and footnote should indicate LOCF for all tables.
- If text wraps across more than one line (for a note), the first letter for all lines of text after the first one will be indented to align beneath the first letter of the text in the first line.
- The page identification in the format Page X of Y (where Y is the total number of pages for the output) should appear in the first footnote, right aligned.
- Ordering of footnotes should be as follows:
 - o 1.) Source data listing reference, if necessary
 - o 2.) Abbreviations and definitions
 - o 3.) Formulae
 - o 4.) P-value significance footnote

- o 5.) Symbols
- o 6.) Specific notes
- Common notes from table to table should appear in the same order.
- The symbols should appear in the same order as what they are defined in the table or listing, from left to right.

PROGRAMMING INSTRUCTIONS

Programming instructions must appear in blue font at the end of each table or listing shell. Programming instructions, where necessary, should follow the table or listing shells in blue font, beginning with the words “Programming Note” followed by a colon. These include notes on the output, reminders of how to handle missing values, repeat shells for similar tables etc.

DATES & TIMES

Depending on data available, dates and times will take the form “yyyy-mm-dd hh:mm”.

SPELLING FORMAT

English US

PRESENTATION OF TREATMENT GROUPS

For outputs, treatment groups will be represented as follows and in the order shown.

Treatment Group	For Tables and Graphs	For Listings (include if different to tables)
AGS-16C3F	AGS-16C3F	
Axitinib	Axitinib	
Total (where applicable)	Total	Not applicable

PRESENTATION OF TIMEPOINTS

For outputs, treatment cycles will be represented as follows and in the order shown. Visits will be displayed as carried in the raw data, unless otherwise specified in the analysis dataset specifications. The number of visits and cycles will vary across subjects.

Long Name	Short Name (default for presentations)
Cycle x Day y	CxDy
Example:	
Cycle 1 Day 1	C1D1
Cycle 1 Day 2	C1D2

LISTINGS

All listings will be ordered by the following (unless otherwise indicated in the template):

- Randomized treatment group (or treatment received if it's a safety output)
- Subject ID
- Date (where applicable)

